8.3.1 Investigator reporting: notifying the study sponsor

Not applicable. The study has no external sponsor.

8.4 Stopping Rules

We do not anticipate significant adverse events. Given no safety data available in the population under study, the research may involve risks that are currently unforeseeable. If any one event is identified that may have caused any type of harm to a participant, study recruitment and associated study activities will be immediately halted until the study team reviews the event and determines if any study procedures need to be revised. Study recruitment and associated study activities will only resume after review of study protocol has been completed and any recommended revisions made as advised by both the study team and the Penn IRB.

8.5 Medical Monitoring

PI [name] will be responsible for overseeing the safety of the study. In addition, Co-I [name] (study physician) and [name] (study lymphedema therapist) will be involved in medical monitoring.

8.5.1 Data and Safety Monitoring Plan

The data and safety monitoring plan will adhere to policy guidance and standards set by the Penn IRB. The PI [name] will be responsible for monitoring the entire study.

Data Management: 1) Self-reported questionnaires will be completed by participants using a tablet to enter their responses into REDCap. The research assistant will review participants' completeness for each questionnaire. If participants prefer or if there are technical difficulties, hard copy forms will be used. All hard copy data will be double-entered into REDCap, checked for discrepancies, and reconciled with hard copy forms. All forms will be stored in a secured cabinet. 2) Physical examination data collected by the study staff will be entered by the research assistant into REDCap. These data will also be double-entered, checked for discrepancies, and reconciled with the hard copy form. 3) Imaging data (digital photos) will be deidentified (white out eyes) and only scoring data will transfer out to REDCap. Data from various sources will be integrated into the study databases by the Data Specialist. All data will be coded without any identifiable information. The PI [name] and the data specialist will monitor and ensure that all data are timely entered into

CONFIDENTIAL

the databases and all protocol specifics are met. PI [name] will monitor all databases monthly and maintain a master table that links participants to ID number in a password-protected database on a secure server throughout the study and after close of study.

Monitoring by the PI: PI [name], with assistance from the Co-I [name], the study lymphedema therapist ([name]), and other study staff members, will monitor all the study activities to ensure safety of participants and integrity of the data collection and management. The research team will meet monthly to discuss recruitment, retention, study progress, and any safety concerns. Any potential issues related to the study activities will be discussed and addressed appropriately and timely. Participants will be educated regarding signs and symptoms related to adverse events requiring urgent or emergent medical care. All adverse events will be documented using CTCAE criteria, reviewed by Drs. [name] and [name]. Any contributing factors will be reviewed. Strategies to prevent further complications will be developed and implemented. Although adverse events are highly unlikely, should they develop, they will be reported to the Penn IRB, within the required time window.

9 Study Administration, Data Handling and Record Keeping

9.1 Confidentiality

All the study data will be stored in a secured network drive managed by University of Pennsylvania School of Nursing IT staff member. All participants will be assigned a study ID number (e.g., 100). Numbers will be assigned by trained study staff. It is important and necessary for the study team to know participants names in order to communicate with them during the study. This information will be maintained in a participant tracking database that is not stored on the hard drive, accessible only to the study team members through a password protected computer and link to a Penn School of Nursing server that is accessible only the study team. The name column will be deleted at the end of the study.

9.2 Data Collection and Management

Data collection will be conducted by a trained staff member at a private room at the Abramson Cancer Center (ACC) HNC clinics (participant recruitment and baseline data collection). The following procedure will be utilized to protect the privacy of the research participant. All data will be coded and filed without any name or other identifiable information. Self-reported questionnaires will be completed by participants using an encrypted and secured tablet to enter their responses into REDCap. The research assistant will review participants' completeness for each questionnaire. If participants prefer or if there are technical difficulties, hard copy forms will be used. All hard copy data will be double-entered into REDCap, checked for discrepancies, and reconciled with hard copy forms. All hard copies will be placed in a locking file cabinet. Only the study team have access to the file cabinet and electronic database. After the study is concluded, the research data will be stored at Penn School of Nursing.

10 Study Monitoring, Auditing, and Inspecting

10.1 Study Monitoring Plan

Monitoring by the PI: The PI [name], with assistance from the Co-I [name], the study lymphedema therapist ([name]), and other study staff members, will monitor all the study activities to ensure safety of participants and integrity of the data collection and management. The research team will meet monthly to discuss recruitment, retention, study progress, and any safety concerns. Any potential issues related to the study activities will be discussed and addressed appropriately and timely. Participants will be educated regarding signs and symptoms related to adverse events requiring urgent or emergent medical care. All adverse events will be documented using CTCAE criteria, reviewed by Drs. [name] and [name]. Any contributing factors will be reviewed. Strategies to prevent further complications will be developed and implemented. Although adverse events are highly unlikely, should they develop, they will be reported to the Penn IRB, within the required time window.

CONFIDENTIAL

10.2 Auditing and Inspecting

The PI [name] will permit study-related monitoring, audits, and inspections by the IRB, government regulatory bodies, and University compliance and quality assurance groups of all study related documents (e.g., source documents, regulatory documents, data collection instruments, study data etc.).

11 Ethical Considerations

Although this is an interventional study, foreseeable physical, psychological, financial, legal, or other risks from study participation are believed to be minimal.

11.1 Risks

1) Physical: No physical risks (e.g., worsening lymphedema or fibrosis) from using LLLT in individuals with breast cancer-related lymphedema have been reported in the known current literature review. No physical risks from using LLLT were reported in the cases studies conducted in individuals with head and neck lymphedema. Subjects will not have any burning sensation, warmth, or any other uncomfortable sensations on the sites treated with low-level laser. Currently, there is no safety data in the population under study. Thus, we will inform participants of reporting any physical damages they have during the course of the study.

2) Psychological: There are no known psychological risks associated with LLLT.

3) Financial: The LLLT will be provided free of charge. Patients may incur expense of gas when driving to the Penn Clinic.

4) Legal: There are no known legal risks.

5) Other: There may be risks that are unknown at this time.

Our planned protections from the above-noted risks are as follows:

1) Physical: Currently, there are no known potential physical risks for being in this study. Given no safety data available in the population under study, the research may involve risks that are currently unforeseeable. To minimize any potential physical risks, the following will be done: a) Participants will be given the study contact phone numbers and emails to ask any questions or to report any unexpected problems if the problems are directly related to the study activities; b) if study staff identify any unanticipated problems, Drs. [name], [name], and study lymphedema therapist ([name]) will be notified immediately. Appropriate evaluation and timely therapy will be provided to the participant. [name], [name], and study lymphedema therapists will determine if participants with significant unanticipated issues will remain on the study based on safety consideration; and c) if anyone experience an adverse event directly related to the study activities that are done for research, they can get reasonable, immediate, and necessary medical care for their adverse events at Penn.

2) Psychological: If study staff identifies participants with significant distress during the course of the study, PI [name] and Co-I [name] will be notified immediately so that appropriate psychological evaluation and referrals will be made. Drs. [name] and [name] will determine if participants with significant psychological issues will remain on study.

3) Financial: The LLLT will be provided free of charge. Patients will incur expense of gas when driving to the Penn Clinic during study follow-up visits. To offset travel/gas cost, participants will be provided a financial token of appreciation for participation in the study.

4) Legal: There are no known legal risks.

5) Other: Should the team become aware of any additional risks, participants will be notified and informed consents will be modified to reflect the new information.

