1.3 Dose Rationale (if applicable)

We propose that participants will receive LLLT twice a week for 6 weeks (12 sessions). This regimen was developed based on the evidence from literature.

2 Study Objectives

The goal of this proposed research is to evaluate the effect of LLLT on facial/neck swelling and fibrotic changes, symptom burden, and neck mobility in HNC survivors with lymphedema through a pilot study.

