3.1 General Design

We will conduct a single-arm, pre-and post-design clinical trial. Outcome measures include: 1) feasibility (barriers to implementation, safety, and satisfaction) of the proposed intervention [Primary aim]; and 2) preliminary efficacy (lymphedema progression, symptom burden, and functional status) of the proposed intervention [Secondary aim]. Study assessments will take place at baseline, immediately after end of the intervention, and 4-week post-intervention.

CONFIDENTIAL

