3.1.2 Study Intervention Phase and Follow Up Phase

After completion of the baseline measures, participants will be scheduled for LLLT. The LLLT includes receiving LLLT twice a week for 6 weeks (12 sessions) (LLL protocol developed based on the literature review³⁴⁻⁴¹). After completion of the 12-session LLLT, participants will be given a) contact information and instructions to call for problems and b) a calendar outlining dates for 4-week follow-up data collection.

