8.2 Recording of Adverse Events

Each contact with the subject, the trained staff will seek information on adverse events by specific questioning and, as appropriate, by examination. Information on all adverse events will be recorded immediately in the source document, and also in the appropriate adverse event module of the case report form (CRF). All clearly related signs, symptoms, and abnormal diagnostic procedures results should be recorded in the source document.

All adverse events occurring during the study period will be recorded. The clinical course of each event will be followed until resolution, stabilization, or until it has been determined that the study intervention or participation is not the cause. Serious adverse events that are still ongoing at the end of the study period will be followed up to determine the final outcome. Any serious adverse event that occurs after the study period and is considered to be possibly related to the study intervention or study participation will be recorded and reported immediately.

All adverse events will be reviewed by Drs. [name] and [name], any contributing factors will be reviewed, and strategies to prevent further complications will be developed and implemented. [name] will meet with study staff monthly to evaluate any other safety concerns. Adverse events will be reported to the Penn IRB within the window required by the IRB. If study staff identify the following unanticipated problems related to the research (e.g., infection in the treated area, sudden increase in swelling), which occur during the study, Drs. [name], [name], and study lymphedema therapists will be notified immediately. Patients will be referred and receive appropriate and timely therapy. Drs. [name] and [name] will determine if participants with adverse events or any unexpected issues will remain on the study based on safety consideration. Drs. [name] and [name] as well as the study lymphedema therapist will evaluate the relationship of each adverse event to the study procedures. PI [name] and Co-I [name] will be responsible for making the determination of the relationship

CONFIDENTIAL

of the adverse event to the study procedures (e.g., definitely related, probably related, possible related, unlikely or unrelated).

8.3 Reporting of Adverse Events, Adverse Device Effects and Unanticipated Problems to Penn IRB and ACC

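### Section 11.1 a) ties participants' own reports to problems directly related to the study, which conflicts with Sections 8.2 and 3.1.2 and may delay or lose some reports between contacts

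*Combined protocol and SAP*

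**What the plan says.** The protocol describes how problems reach the study team in several places, and they do not agree.

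- **Section 11.1, planned protections, Physical, item a):** participants receive phone numbers and emails to ask questions or "to report any unexpected problems if the problems are directly related to the study activities".
- **Section 11.1, Physical risks, earlier in the same section:** "we will inform participants of reporting any physical damages they have during the course of the study". There is no condition on cause.
- **Section 3.1.2:** after the 12 sessions, participants are given "contact information and instructions to call for problems". Again there is no condition.
- **Section 8.2, scope:** "All adverse events occurring during the study period will be recorded".
- **Section 8.2, method:** at each contact, "the trained staff will seek information on adverse events by specific questioning and, as appropriate, by examination".
- **Section 8.2, causality:** the PI and Co-I "will be responsible for making the determination of the relationship" of each event to the study procedures.

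Safety is a component of the primary endpoint (Section 3.2.1). Section 7 summarises adverse events descriptively, with no threshold or test. Sections 8.4 and 11.1 both state that no safety data exist in this population.

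**The concern.** Item a) asks the participant to decide on causality before making contact. Section 8.2 gives that decision to the PI and Co-I, after the event has been recorded. A participant who follows item a) to the letter would not report a problem that he or she puts down to something else. Section 11.1 also says that treatment causes no uncomfortable sensation and that no physical risk is known. If participants are told the same, some would have reason to put a new problem down to another cause.

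Any error goes one way, towards fewer recorded events, in the first safety data for this population. Timing matters too: the review in 8.2 and the halt in 8.4 act only on events that the team has identified.

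**Working it through.** The plan gives no adverse event rate, safety threshold or sample size calculation, so there is no figure to reproduce. The check has two parts: where the condition can act, and an illustration on assumed values.

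**1. Where the condition can act**

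| Period or group | Scheduled contact | Can item a) matter? |
|---|---|---|
| Weeks 1–6 | 12 sessions, two per week (1.3), with questioning at each contact (8.2) | Little: the next questioning is days away |
| End of intervention | Assessment visit (3.1, 6.2.2) | No: staff ask directly |
| The 4 weeks after | None until the 4-week visit (3.1, 6.2.3) | Yes: until then an event reaches staff only if the participant makes contact; after that, capture rests on recall |
| Left before completing 12 sessions | 6.3 describes no later safety contact | Yes: the 3.1.2 instruction comes only after the 12 sessions, so this group may not receive it |
| Lost between the last session and the 4-week visit | None | Partly: they should have the unconditional 3.1.2 instruction, but also the conditional one in 11.1 a) |

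The follow-up interval is 4 of 10 weeks (4.4), or 40% of participation. Section 7 expects at least 80% to complete study activities. Up to 25 × 0.20 = 5 participants could therefore fail to complete with that criterion still met.

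**2. Illustration of size**

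From the documents: n = 25 (4.5) and a follow-up share of 4/10 = 0.40. Assumed, with no source in the documents: a true event rate r per participant, independence between participants, events spread evenly over 10 weeks, and a fraction f of follow-up events never captured.

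- Overall loss = 0.40 × f
- Observed rate r′ = r × (1 − 0.40 f)
- P(no event seen) = (1 − r′)^25

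| r | f | Overall loss | r′ | P(no event seen) |
|---|---|---|---|---|
| 8% | 0 | 0% | 0.080 | 0.92^25 = 12% |
| 8% | 1/4 | 10% | 0.072 | 0.928^25 = 15% |
| 8% | 1/2 | 20% | 0.064 | 0.936^25 = 19% |
| 12% | 0 | 0% | 0.120 | 0.88^25 = 4% |
| 12% | 1/4 | 10% | 0.108 | 0.892^25 = 6% |
| 12% | 1/2 | 20% | 0.096 | 0.904^25 = 8% |

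These rows show the effect of follow-up events being lost for any reason. Only part of such a loss could come from the clause; the rest would be recall and dropout. If events cluster during treatment, the effect is smaller. Early leavers are not modelled.

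A much larger loss does not fit this mechanism. With events spread evenly, missing every follow-up event loses 40%. An overall loss of 25% would need 0.25 / 0.40 = 62.5% of follow-up events to stay uncaptured even after direct questioning at the 4-week visit.

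**The case against.** The strongest reply is that participants' own calls are not the main route. Trained staff question participants at every contact. The 4-week visit includes a physical examination and symptom questionnaires, so follow-up events are still sought. Section 3.1.2 gives an unconditional instruction for just that interval, and Section 8.1 adds education on signs that need urgent care. Item a) stands in a list of ethical protections, not in the procedure for collecting adverse events. Deleting it would cure neither four-week recall nor loss to follow-up. No stated decision depends on seeing zero events: the numerical feasibility criteria in Section 7 concern completion and satisfaction.

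Most of this stands, and it rules out a stronger reading. A reader might infer that participants are told to report only related problems, and that the primary safety result is therefore biased. The documents do not support that. Item a) does not say only, the same section contains an unconditional instruction, and active questioning does not depend on what participants choose to report. The consent pages are also not in the review copy, so what participants are actually told cannot be checked.

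Three things remain. The two instructions in 11.1 conflict. Questioning at a later visit can recover an event but not the time lost before review. And those who leave before completing 12 sessions may not receive the instruction in 3.1.2.

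**Conclusion.** The inconsistency is real and its reach is narrow. Item a) of 11.1 conflicts with 8.2 on what is recorded and on who judges cause, and with the unconditional wording in 3.1.2 and in 11.1 itself. The effect is confined to reports that participants start between contacts, and to those who withdraw or are lost before the next contact. In those cases reports may come late or not at all, and the direction is always towards fewer events.

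The documents do not allow the size to be derived. On the assumed values above, the change in the chance of a clean safety record is a few percentage points: 12% to about 15–19% at an 8% rate. That shows a possible order of magnitude and is not an estimate of bias. Severity is minor.

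**What to change.** In Section 11.1, item a), delete the condition that the problem be directly related to study activities. The item would then ask participants to report any new or worsening problem during the study, whatever they think caused it. Relatedness is judged afterwards by the persons named in 8.2. Make the same deletion in any participant material that repeats the clause.

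Item c) of the same list, which concerns access to medical care, uses similar words but is not part of this point.

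The cost is one clause, matching edits to participant material if it repeats the clause, and a few more unrelated events in the log. No change to the analysis or the sample size follows.

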11.2 Benefits

Potential benefits to the individual: Although the potential direct benefit to study participants is unknown, individual participants will be exposed to and have increased knowledge about lymphedema and fibrosis. Participants may have positive feelings about participation in a research program that may benefit others.

CONFIDENTIAL

Potential benefits to human kind: Possible future benefits for HNC survivors are potentially substantial. If we are able to demonstrate that LLLT is safe, feasible and effective in HNC patients, we will be adding to the armamentarium of an alternative intervention that can diminish progression of lymphedema and fibrosis, decrease symptom burden, increase function, and improve overall quality of life.

11.3 Risk Benefit Assessment

Currently, there are no known potential risks for being in this study. Given no safety data available in the population under study, the research may involve risks that are currently unforeseeable. As noted above, potential benefits are reasonable and substantial. Thus, based on the risk benefit assessment, it appears to be acceptable for this research within human subjects.

11.4 Informed Consent Process / HIPAA Authorization

Once the study is approved by the Penn IRB and the ACC, the trained study team members will meet with potential participants who express interest in the study. Potential study participants will be provided one copy of the informed consent to read and review. Study team members will review the study procedures and activities with potential participants. The informed consent document will be written in lay language and cover all study activities participants will engage in during the study, define the length of time the study will be conducted, and provide instructions for participant withdrawal from the study should they choose to do so. Study staff will review and, when necessary, read the informed consent document to potential participants. Participants will be given ample time and opportunity to ask questions, and all questions will be answered by study staff. The consent process will take place in a private location, with a closed door. Once participants have had an opportunity to ask questions, those questions have been answered, and they indicate an interest in participation, they will be asked to sign a written informed consent document as the study staff witnesses. In addition, the participant will be given a copy of informed consent signed by both the participant and study staff. We will not seek waivers of the informed consent process.

12 Study Finances

